1.2 Background Information on Investigational Medicinal Product

The investigational medicinal product (IMP) to be tested in this study is teverelix trifluoroacetate (TFA), a depot formulation of a GnRH antagonist used for the treatment of advanced prostate cancer. Treatment with the IMP will start with a loading dose administered

Page 28 of 84

through 2 injections, one of which will be given IM and the other of which will be given SC, followed by a maintenance SC injection every 4 or 6 weeks. Two treatment regimens will be tested in this study: 120 mg of teverelix TFA administered, after the loading dose, every 42 days and 180 mg of teverelix TFA administered, after the loading dose, every 42 days.

1.2.1 Preclinical Studies

In preclinical studies, teverelix has been shown to exert anti-ovulatory activity and to inhibit LH, FSH and T secretion.

No target organ toxicity was observed from subacute and chronic toxicity studies in rats and dogs following SC administration of teverelix and no adverse systemic effects have been demonstrated. In general, treatment-related effects were considered to be either physiological changes arising as a result of the pharmacological response to administration of a GnRH antagonist, or foreign body inflammatory reactions at the injection site arising as a result of the physical nature of the test material, rather than a direct toxic response to teverelix. The most notable finding across species and studies was the clear reduction in reproductive organ and accessory gland weight, confirmed pathologically as arrested development or degeneration. Notable findings in males were spermatogenic arrest within the testes, ductal/tubular atrophy, absence of spermatozoa within the epididymides, and prostate gland atrophy. In females, atrophy of the vagina, cervix and uterus, maturation arrest within the ovaries, and atrophy of mammary gland tissue were apparent.

Injection site reactions (ISR) were noted during dose range finding studies and were cited as the limiting factor in the selection of high doses for the definitive repeat dose toxicity studies. In the rat and dog, daily SC administration of teverelix at a concentration of 10 mg/mL (doses of up to 50 mg/kg in the rat and 20 mg/kg in the dog) was unsuitable and led to unacceptable ISRs, which were considered to be a function of the physical characteristics of the test substance, the dosing regime, and the dose volume. SC doses of up to 20 mg/kg/day using a concentration of 75 mg/mL were tolerated, demonstrating that reducing the dose volume and using a higher concentration to achieve the same dose ameliorated the local response. Weekly dosing for up to 6 months in rats and 9 months in dogs using a 75 mg/mL (in 5% mannitol) formulation was associated with some evidence of clinical ISRs, but overall, dosing was tolerated. Pathologically, signs of an infilammatory response within the SC tissue, predominantly consisting of an infiltration of macrophages (foreign body-type response), was apparent.

Early screening studies indicated that teverelix acetate was devoid of anaphylactoid reactions when administered intravenously in rats (single dose 5 mg/kg) or other species including mice, rabbits, and dogs. Teverelix also had very modest histamine-releasing properties on rat mast cells. When intravenous (IV) teverelix acetate was administered to rats and cynomolgus monkeys in toxicity studies, clinical signs indicative of release of vasoactive chemical modulators were seen and some animals were found dead following administration of the highest dose. Subsequent studies with teverelix TFA administered by the SC route, which is relevant to the clinical situation, did not identify any signs of anaphylaxis or histamine release, and no effects on blood pressure [BP] were apparent. Even a single and repeat dose of 50 mg/kg administered by the SC route to rats did not induce adverse clinical signs and teverelix showed no mutagenic or clastogenic potential.

Given the pharmacological effect of teverelix on pituitary gonadotrophic hormones, a reduction in fertility is anticipated. However, studies have been conducted to determine whether restoration of fertility is seen post-dosing. A single dose of 2 mg/kg administered to male rats resulted in reduced plasma T concentrations for 5 weeks after dosing, but there was

Page 29 of 84

no subsequent effect on mating performance or pregnancy outcome 11-, 14- or 17-weeks post-dosing. A single dose of 2 mg/kg administered to female rats had no effect on oestrous cyclicity 5/6 weeks post-dosing, and no effect on the capability of the females to become pregnant 12 weeks post-dosing. Lower numbers of corpora lutea, implantations, and live foetuses and a higher number of early intra-uterine deaths were consistent with the known pharmacological effect.

In embryofoetal/teratogenicity studies, an increase in post-implantation loss was noted following administration of 15 μ g/kg in the rabbit but no embryotoxicity was seen up to a dose of 10 μ g/kg in the rat. No evidence of teratogenicity was found in either species [11].

1.2.2 Clinical Studies

In Phase 1 clinical studies conducted in healthy men, teverelix produced a rapid, marked suppression of serum levels of LH, T, and to a lesser extent FSH. In the first Phase 1 studies, the teverelix-induced T suppression was fully reversible within 1 week. In higher dose Phase 1 studies, some patients had persistent T suppression for several months. A Phase 1 clinical study conducted in healthy women demonstrated that teverelix TFA reduced the serum levels of LH, FSH, oestradiol, and progesterone in a dose-dependent manner. As early as 2 weeks after administration of two 60 mg teverelix TFA injections in participants with benign prostatic hyperplasia (BPH), a statistically significant decrease was observed in prostatic symptoms, as measured by the International Prostate Symptom Score (I-PSS). Symptomatic improvement increased over time, and was most pronounced at study completion (16 weeks). A total of 83% of participants who received teverelix TFA were classified as responders (defined as a >3 point reduction in symptom score from baseline). In addition, statistically significant improvements were observed in maximum urine flow rate, Quality of Life (QoL) and prostate size when compared to baseline. In a subsequent study, where participants were administered a single injection of 30 mg teverelix TFA, 60 mg teverelix TFA or placebo, a larger increase in maximum urinary flow rate occurred in both the 30 mg and 60 mg teverelix TFA treatment groups compared to placebo. In addition, a significant increase from baseline for mean urinary flow rate was observed in the 60 mg teverelix TFA treatment group, and the 30 mg teverelix TFA group was more than 3 times as likely to give a favourable QoL response compared to placebo. In the extension study, participants administered a second dose of either 30 mg or 60 mg teverelix TFA experienced an increase in mean and maximum urinary flow rate, compared to the placebo treated group, and were more likely to give a favourable response with respect to QoL. In the case of advanced prostate cancer, suppression of T to castration levels (<0.5 ng/mL)

In the case of advanced prostate cancer, suppression of T to castration levels (<0.5 ng/mL) was achieved within 3 days in the majority of the participants and this was maintained for 4 to 8 weeks. Some participants experienced transient castration breakthrough, where T concentrations temporarily increased to ≥0.5 ng/mL. Teverelix TFA was also shown to rapidly reduce and normalise PSA levels.

Pharmacokinetic (PK) and pharmacodynamic (PD) data from 2 studies indicate that the SC route of administration for teverelix TFA produces a more sustained suppression of T levels than the IM route. No safety concerns were identified in any of the conducted clinical studies. The most frequently reported adverse events (AEs) were mild ISRs and reversible symptoms characteristic of T and oestrogen deprivation, such as hot flushes, decrease in libido and potency, and reduction in testis size. No serious adverse events (SAEs), considered to be at least possibly related to the administration of teverelix TFA, have been reported [11].

ANT-1111-02, Teverelix TFA in Prostate Cancer FINAL Version 5.0, 31 May 2022 Page 30 of 84

1.2.3 Risk-benefit Assessment

No SAEs assessed as attributable to the administration of teverelix TFA have been reported. Three SAEs have been reported for teverelix TFA participants to date and none of these was thought to be related to IMP (SAE 1, jaundice cholestatic/cholelithiasis/bile duct stone/pancreatitis; SAE 2, worsening ischaemic heart disease/atrial fibrillation; SAE 3, nephrolithiasis).

The most frequently reported AEs were mild ISR and reversible symptoms characteristic of T and oestrogen deprivation, such as hot flushes, decrease in libido, erectile disorder, and reduced testes size. No signs indicative of allergic reactions have been noted in the clinical participants dosed with teverelix TFA to date.

The studies conducted so far have demonstrated no safety concerns and, in the later studies, castration levels of sex hormones in men were obtained within a few days. Teverelix TFA reduced the serum levels of LH, FSH, oestradiol, and progesterone in a dose-dependent manner in healthy women. Statistically significant improvements in symptoms were achieved in participants with BPH, and PSA levels were normalised in participants with advanced prostate cancer [11].

1.3 **Study Rationale**

As an GnRH antagonist, teverelix antagonises the GnRH by reversibly binding to GnRH receptors in the pituitary gland. This subsequently blocks the action of GnRH in the body and the release of both LH and FSH from the pituitary gland, which leads to a rapid suppression of T release from the testes.

Antev Ltd has conducted a Phase 1, open-label, single centre study investigating the PK, safety, and PD of a single dose of teverelix TFA administered either SC or IM to healthy male volunteers. The doses and administration schedule of teverelix TFA used in this Phase 2 study are based on the PK and PD results of the above-mentioned Phase 1 study.

The study population planned for this Phase 2 study is comparable to that of the previously conducted Phase 2 study for the development of degarelix, which has been approved by the FDA and the European Medicines Agency in 2008 based on the data from the pivotal study [2].

2 Study Objectives and Purpose

Primary Objective

To assess the efficacy of teverelix TFA in terms of ability to suppress serum T levels to below castration level (<0.5 ng/mL or 1.73 nmol/L) at Day 28.

Secondary Objective(s)

- To assess the efficacy of teverelix TFA in terms of ability to suppress serum T levels to below castration level (<0.2 ng/mL or 0.6934 nmol/L) at Day 28
- To assess the efficacy of teverelix TFA in terms of ability to suppress serum T levels to below castration level (<0.5 ng/mL or 1.73 nmol/L) at Day 42
- To assess the efficacy of teverelix TFA in terms of ability to suppress serum T levels to below castration level (<0.2 ng/mL or 0.6934 nmol/L) at Day 42
- To assess the efficacy of teverelix TFA in terms of ability to suppress serum T levels to below castration level (<0.5 ng/mL or 1.73 nmol/L) at Day 168
- To assess the efficacy of teverelix TFA in terms of ability to suppress serum T levels to below castration level (<0.2 ng/mL or 0.6934 nmol/L) at Day 168

Page 31 of 84

- To assess the efficacy of teverelix TFA in terms of ability to maintain suppression of serum T levels below castration level (<0.5 ng/mL or 1.73 nmol/L) over time during Stage 2 (maintenance-dose period) of the study
- To assess the efficacy of teverelix TFA in terms of ability to maintain suppression of serum T levels below castration level (<0.2 ng/mL or 0.6934 nmol/L) over time during Stage 2 (maintenance-dose period) of the study
- To assess the time taken to achieve serum T levels below castration level (<0.5 ng/mL or 1.73 nmol/L)
- To assess the time taken to achieve serum T levels below castration level (<0.2 ng/mL or 0.6934 nmol/L)
- To assess the time taken to achieve serum T levels above castration level (≥0.5 ng/mL or or 1.73 nmol/L)) following the final, Day 168 injection of teverelix TFA
- To delineate the PK profile of teverelix TFA
- To assess the effects of teverelix TFA on:
 - PSA
 - T
 - FSH
 - LH
- To assess the predictive effect for new cardiovascular (CV) events of cardiac biomarkers:
 - N-terminal pro-B-type natriuretic peptide (NTproBNP)
 - D-dimer
 - C-reactive protein (CRP)
 - high-sensitivity troponin (hsTn)
- To assess the safety of teverelix TFA in terms of:
 - local tolerability (injection site reactions [ISR])
 - systemic tolerability (adverse events, vital signs, electrocardiograms (ECG), Holter monitoring (subset of 30 subjects in Group 2 only) and laboratory parameters)

3 Overall Study Design and Plan Description

3.1 Core Study

This is an adaptive Phase 2, open-label, multicentre study to evaluate the PK, PD, efficacy and safety of teverelix TFA, a GnRH antagonist in participants with advanced prostate cancer.

For Group 1, it is planned to enrol approximately 24 participants from 3 investigational sites in Lithuania to obtain 20 evaluable participants with prostate advanced cancer. For Group 2, it is planned to enrol approximately 60 participants from up to 7 investigational sites in Lithuania and (potentially) Netherlands/Belgium in order to obtain 50 evaluable participants with advanced prostate cancer, for the assessment of treatment response on Day 28 and throughout the study up to Day 168.

Figure 1 displays the study design.

The study consists of the following periods/visits:

Page 32 of 84

NTEV

Screening Period: Day -6 to -1 **Groups 1 & 2 Treatment Period:**

Stage 1: Loading dose administered at baseline (Day 0) with follow-up visits until Day 28

Stage 2: Maintenance treatment administered every 6 weeks with visits from Day 28 up to Day 168, or until treatment ceases to become effective

Follow-up Visit: 28 days after the last dose of IMP

Group 2 (Stage 3 subjects only) Treatment Period:

Stage 1: Loading dose administered at baseline (Day 0) with follow-up visits until Day 28

Stage 2: Maintenance treatment administered every 6 weeks with visits from Day 28 up to Day 168, or until treatment ceases to become effective

[figure not shown]
Stage 3: Follow up period. Day 203 visit followed by weekly visits until Day 252 or until serum T levels are ≥ 1 ng/mL (local lab result), whichever occurs first Follow-up Visit: Day 259 or ≥ 7 days after serum T levels are ≥ 1 ng/mL (local lab result), whichever occurs first

An overview of the Schedule of Assessments is provided in Section 7.1. After signing the informed consent for the core study, participants will undergo a screening examination within 6 days prior to the administration of teverelix TFA to verify the participants' eligibility, and to document participant characteristics, including medical and surgical history, and disease characteristics.

Table 1 presents the 2 dosing regimens to be evaluated in this study.

Figure 1: Study Design

TEVERELIX IN ADVANCED PROSTATE CANCER PHASE 2 **STUDY PROGRESSION**

ANT-1111-02, Teverelix TFA in Prostate Cancer

FINAL Version 5.0, 31 May 2022

Page 33 of 84

Table 1: Dosing Regimens under Evaluation

_Group	Loading Dose	Maintenance Dose	Dosing Interval
1	120 mg IM +120 mg SC	120 mg SC	6 weekly
2	180 mg IM +180 mg SC	180 mg SC	6 weekly

IM=intramuscular; SC=subcutaneous

Initially enrolment will open for Group 1 only. If, after Day 28, a participant's serum T value (as tested by the local laboratory on Day 21) is >2 ng/mL, the participant will be withdrawn from the study.

Enrolment will continue for Group 1 until 20 participants have completed the Day 28 visit with no more than 2 participants being classified as a treatment failure. Treatment failure is defined as having a T level >2 ng/mL at Day 28 (as tested by the local laboratory on Day 21) or requiring to be withdrawn at any later timepoint during the study.

If 3 or more participants fail treatment in Group 1 then further enrolment into that group will stop due to statistical confidence that a 90% responder rate cannot be achieved with that dosing regimen. All future participants will be enrolled into Group 2.

If in Group 2 at Day 28, a participant's serum T value (as tested by the local laboratory on Day 21) is >2 ng/mL, the participant will be withdrawn from the study.

If 7 or more participants fail in Group 2 then all further enrolment will be stopped and the study will be terminated.

3.2 Discussion of Study Design

Teverelix is currently being developed for chemical castration in participants with advanced prostate cancer. Five previous Phase 1 clinical studies of teverelix have been conducted in healthy male volunteers as well as 5 Phase 2 clinical studies in prostate cancer patients. In these studies, teverelix TFA depot formulation has been tested following administration by single and multiple (2) SC injection(s) at doses of 10 mg, 30 mg, 60 mg, 120 mg or 180 mg. Teverelix produced a rapid, marked suppression of serum levels of LH, T and, to a lesser extent, FSH. The teverelix TFA-induced hormone suppression demonstrated in these studies was fully reversible within 1 week and exhibited no signs of a weight effect. Overall, teverelix TFA was safe and well tolerated.

Three Phase 2 studies in participants with BPH have been conducted as well. In participants with BPH, a statistically significant decrease was observed in prostatic symptoms as early as 2 weeks after administration of teverelix TFA. Symptomatic improvement increased over time and was most pronounced at study completion (after 16 weeks). A total of 76% of participants on teverelix TFA were classified as responders.

For participants with APC suppression of T below castration level, this was achieved within 3 days and was maintained for 4 to 8 weeks. Teverelix TFA was also shown to rapidly reduce and normalise PSA levels. In the Phase 1 and 2 studies a small number of study subjects (0.6 to 1.5%) experienced transient elevated liver function enzymes. Standard monitoring of liver function enzymes is recommended for future clinical studies.

PK and PD data from 2 different studies indicate that the SC route of administration of teverelix TFA produces a more sustained suppression of T levels than the IM route. This appears to be due to the fact that the SC route is more effective at maintaining adequate systemic levels of teverelix TFA.

In this study, teverelix TFA is being tested in participants with APC with a loading dose regimen administered as 2 doses of 120 mg each, given IM and SC, followed by SC injections of 120 mg of teverelix TFA every 6 weeks thereafter, as the preferred treatment regimen. If this treatment schedule fails to induce castration levels of T (≤2 ng/mL), an

Page 34 of 84

alternative treatment option will be tested: 180 mg each of teverelix TFA, given IM and SC, followed by SC injections of 180 mg of teverelix TFA every 6 weeks thereafter, for a total duration of 168 days. As this is a Phase 2 study to evaluate the dosage and effectiveness of teverelix TFA in the suppression and maintenance of serum T concentrations below castration levels, an open-label, non-controlled study design has been chosen.

4 Selection of Study Population

In this study, approximately 24 participants from Group 1, or 60 participants from Group 2 will be recruited from 7 up to study centres in Lithuania and potentially Netherlands and/or Belgium in order to provide a sample size of 20 participants from Group 1, or 50 participants from Group 2. These participants will comprise the per-protocol (PP) analysis set for evaluation of treatment response at Day 28 and throughout the study up to Day 168. As soon as this number of enrolled participants is reached, no more participants will be recruited. Enrolled participants who cannot be analysed in the PP analysis set will not be replaced. The participants for this study will be recruited from inpatient/outpatient departments of clinics/hospitals and/or general practitioners/specialists. If inpatients are included in the study, they will receive further treatment as inpatients.

4.1 **Participant Inclusion Criteria**

The participant is allowed to participate in the study if ALL of the following criteria are fulfilled:

- 1. Is male, aged \leq 85 years (\geq 18 years) at the beginning of the treatment period (Day 0)
- 2. Has histologically proven advanced adenocarcinoma of the prostate (metastatic or non-metastatic hormone-sensitive non-curative), suitable for ADT
- 3. Is treatment naïve for any of the following:
 - a. GnRH analogues
 - b. Androgen receptor antagonists, or
 - c. Androgen synthesis inhibitors (e.g. abiraterone)
- 4. Agrees to practice contraception during the entire study treatment period and for 3 months after the last dose of IMP is administered:
 - a. Either by using double barrier contraception,
 - b. or, is truly sexually abstinent, when this is in line with the preferred and usual lifestyle of the participant

Note: Periodic abstinence [e.g. calendar, ovulation, symptothermal, postovulation methods for the female partner with childbearing potential] and withdrawal are not acceptable methods of contraception.

5. Has provided written (personally signed and dated) informed consent before completing any study-related procedure, which means any assessment or evaluation that would not have formed a part of his normal medical care

4.2 Participant Exclusion Criteria

If any of the following criteria apply, the participant MUST NOT be admitted to the study. The participant:

1. Has abnormal screening and/or baseline laboratory values that suggest a clinically significant underlying disease, or the following laboratory values:

- a. Liver function test (aspartate aminotransferase [ASAT/SGOT], alanine aminotransferase [ALAT/SGPT]), or total bilirubin exceeding twice the upper limit of the normal (ULN) range
- b. Creatinine twice the ULN range
- c. Uncontrolled diabetes (HbA1c >7.5%) or previously undiagnosed diabetes mellitus with HbA1c >6.5%
- 2. Has any contraindication to the use of teverelix TFA
- 3. Has a life expectancy of less than 1 year
- 4. Has T levels <2.0 ng/mL at screening
- 5. Has a medical history of bilateral orchidectomy
- 6. Using any of the following prohibited treatments:
 - a. Within 25 weeks prior to screening: dutasteride
 - b. Within 12 weeks prior to screening: finasteride
 - c. Current use of any of the following:
 - i. Anti-androgen therapy, including T replacement therapy and 5α -reductase inhibitor treatment etc. (Spironolactone is a permitted concomitant treatment)
 - ii. Any other medication or herbal product that may affect hormone levels and might, therefore, confound interpretation of the study results (e.g. St. John's wort)
- 7. Has neurological disease, psychiatric disease, drug or alcohol abuse, which could interfere with the participant's proper compliance
- 8. Has a history of myocardial infarction, unstable symptomatic ischaemic heart disease, any ongoing cardiac arrhythmias of grade >2 (chronic stable atrial fibrillation on stable anticoagulant therapy is allowed), thromboembolic events (e.g. deep vein thrombosis, pulmonary embolism, or symptomatic cerebrovascular events), or any other significant cardiac condition (e.g. pericardial effusion, restrictive cardiomyopathy) within 6 months before screening
- 9. Has congenital long QT syndrome or ECG abnormalities at screening of:
 - a. Q-wave infarction, unless identified ≥6 months before screening
 - b. Fridericia corrected QT interval (QTcF interval) >480 msec. If QTcF is prolonged in a participant with a pacemaker, the participant may be enrolled in the study upon discussion with the project clinician
- If the QTcF interval is 450-480 msec, inclusive, in a participant with current use of medications with known effects on QT interval, the participant may be enrolled in the study following discussion with the Medical Lead

Note: Cardiac arrhythmia grading:

- o Bradyarrhythmias (HR <60/min)
- o Tachyarrhythmias (HR >100/min)
- o Supraventricular arrhythmias arrhythmias that originate in the sinoatrial node, atrial myocardium or atrioventricular node (regular QRS complex)
- o Ventricular arrhythmias arrhythmias that originate below the atrioventricular node (wide QRS complex)
- 10. Has known or suspected severe renal impairment
- 11. Has a medical history of diagnosis of, or treatment for, another malignancy within 2 years before the first dose of IMP, or previous diagnosis of another malignancy with

Page 36 of 84

- evidence of residual disease. Participants with nonmelanoma skin cancer or carcinoma in situ of any type are not excluded if they have undergone complete resection
- 12. Is currently using Class IA (e.g. quinidine, procainamide) or Class III (e.g. amiodarone, sotalol) antiarrhythmic medications
- 13. Has uncontrolled hypertension despite appropriate medical therapy (sitting BP of >180 millimetres of mercury [mmHg] systolic and >95 mmHg diastolic at 2 separate measurements taken no more than 60 minutes apart during the screening visit). Participants with isolated systolic BP measurements >180 mmHg may be rescreened. Participants with isolated systolic BP measurements 141 to 180 mmHg or isolated diastolic BP measurements ≥95 mmHg, although eligible, should be referred for further management of hypertension if indicated
- 14. Has known, previously diagnosed human immunodeficiency virus (HIV) infection, active chronic hepatitis B or C, life-threatening illness unrelated to prostate cancer, or any serious medical condition that could, in the investigator's opinion, potentially interfere with participation in this study. Specific screening for chronic viral illness is at the discretion of the site and/or local Institutional Review Board (IRB)
- 15. Has been exposed to another investigational drug within the 3 months prior to screening
- 16. Has anticipated non-availability for study visits/procedures
- 17. Plans to undergo surgery during the study period
- 18. Known presence of hepatic metastases

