**Table 15 ECG Parameters**

ECG Parameters (Unit)
Conduction Times
Ventricular Rate (msec)
QT Interval (msec)
QTcF Interval (msec)

Note: QTcF = QT/CubeRootRR(seconds)

Thresholds for a significant QTcF prolongation are defined as follows:

- QTcF >450 ms
- QTcF >480 ms
- QTcF >500 ms
- An increase from baseline of >30 ms
- An increase from baseline of >60 ms
- QTcF >500 ms or an increase from baseline of >60 ms.

For the qualitative ECG parameters (morphology), it will be recorded whether the parameter at the specific visit was 'Normal' or 'Abnormal'. Each collected quantitative (conduction times) ECG parameter will be classified as 'Normal' or 'Abnormal' at each visit. For all abnormal values, clinical significance (as determined by the Investigator) and any ECG findings should be indicated.

---

Document:

C:\ProgramData\activePDF\Temp\DocConverter\API\Input\\$651f4dc0b253\$FE3041C5883446E892B20AB6D3F0E1BD.docx

Author: [name]

Version and Date: Version 1.0, 21 Apr 2023

Page 41 of 66

---

Based on the criteria presented in Attachment 2, markedly abnormal ECG parameters will be identified at each visit.

---

Document:

C:\ProgramData\activePDF\Temp\DocConverter\API\Input\\$651f4dc0b253\$FE3041C5883446E892B20AB6D3F0E1BD.docx

Author: [name]

Version and Date: Version 1.0, 21 Apr 2023

Page 42 of 66

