**6.9.4 Electrocardiogram (ECG) Parameters**

ECG Parameters include collected and derived quantitative and qualitative parameters. Qualitative parameters will be summarised by absolute counts (n) and percentages (%). Percentages will be based on the number of subjects with data.

The number and % of patients with markedly abnormal results will be presented for each visit. The Investigators overall assessment will be summarised as a categorical variable along with the shift from baseline in the investigator's overall assessment.

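### The SAP's absolute QTcF thresholds carry no baseline condition, so their counts would mix new prolongation with prolongation present at enrolment

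*Protocol*

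**What the plan says.** **Eligibility.** Protocol 4.2, criterion 9b, excludes at screening a "Fridericia corrected QT interval (QTcF interval) >480 msec. If QTcF is prolonged in a participant with a pacemaker, the participant may be enrolled" once the project clinician has been consulted. No upper limit accompanies that exception. A further bullet covers men on QT-affecting drugs ("If the QTcF interval is 450-480 msec, inclusive, in a participant with current use of medications with known effects on QT interval"), who may enter after discussion with the Medical Lead. A man in the same range who takes no such drug meets no QTcF exclusion. SAP 4.3.3 repeats these criteria.

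**Definition of prolongation.** Under Table 15, SAP 4.2.7 states: "Thresholds for a significant QTcF prolongation are defined as follows". Six criteria follow:

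- three absolute values: >450, >480 and >500 ms;
- two changes: "An increase from baseline of >30 ms" and "An increase from baseline of >60 ms";
- one composite: above 500 ms, or a rise above 60 ms.

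The absolute values, and the >500 ms limb of the composite, carry no baseline condition.

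**Tabulation.** SAP 6.9.4 says: "The number and % of patients with markedly abnormal results will be presented for each visit". It gives a shift from baseline for the investigator's overall assessment only. Protocol 8.1.5 plans descriptive statistics, changes from baseline and shift tables for the 12-lead ECG parameters, with the shifts set against normal ranges.

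**The concern.** The entry rule and the safety thresholds overlap. A man can be eligible at a QTcF that the SAP calls significant prolongation, and he will go on meeting that criterion if nothing changes. The absolute criteria alone cannot show whether a man crossed a threshold on treatment or was already above it.

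This matters more than usual because the study has no control arm to show the background frequency. The Holter recording, which serves the concentration-QTc modelling, covers 30 Group 2 men over 24 hours from Day 0. From Day 28 to follow-up, the scheduled 12-lead ECGs are the planned QT data. With about 60 men in Group 2, a few carried-over cases would visibly move a percentage.

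**Working it through.** The plan states no figure to reproduce here. The check applies the six criteria of SAP 4.2.7 to baseline and post-dose pairs that the entry rules allow. Baseline is the last non-missing pre-dose value (SAP section 4). The values are hypothetical.

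**Step 1. Criteria met by each pair** (b = baseline, v = post-dose, d = v − b, all in ms)

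| b → v | d | Criteria met |
|---|---|---|
| 450 → 450 | 0 | none |
| 470 → 470 | 0 | >450 |
| 480 → 480 | 0 | >450 |
| 510 → 510 (pacemaker) | 0 | >450, >480, >500, composite |
| 445 → 470 | +25 | >450 |
| 480 → 485 | +5 | >450, >480 |
| 470 → 502 | +32 | >450, >480, >500, rise >30, composite |
| 420 → 485 | +65 | >450, >480, rise >30, rise >60, composite |

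Two things follow. An unchanged value can meet absolute criteria, and the composite if it is already above 500. And 470 → 470 and 445 → 470 give the same pattern, although only the second man crossed 450 ms after dosing.

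**Step 2. When a new crossing escapes both change criteria.** For a threshold c, a new crossing means b ≤ c < v. It misses the >30 ms criterion, and so also the >60 ms criterion, when v ≤ b + 30. Both can hold only if c − 30 < b ≤ c:

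- c = 450: baseline above 420 and up to 450;
- c = 480: baseline above 450 and up to 480;
- c = 500: baseline above 470 and up to 500.

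The first two ranges lie within what criterion 9b admits generally. The third does so up to 480, and beyond that through the pacemaker exception.

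**Step 3. Do the planned shifts fill the gap?** SAP 6.9.4 shifts only the investigator's overall assessment. Protocol 8.1.5 shifts ECG parameters against normal ranges, which would not show crossings of 480 or 500 ms. Elsewhere the SAP is more explicit: 6.9.3 names normal-range shift tables for haematology and biochemistry, and 6.9.5 names changes from baseline for vital signs. SAP 7.1 does not say that the protocol's ECG shift tables were dropped.

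**Step 4. Scale, under an assumption.** The documents do not say how many men have a baseline QTcF above 450 ms. Assume 5% to 20% of 60:

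- 0.05 × 60 = 3 and 0.20 × 60 = 12 men meet >450 ms at each visit if nobody changes.
- At 10%, 6/60 = 10.0% (Clopper-Pearson 95% CI 3.8% to 20.5%).
- Counting only the 60 − 6 = 54 men at or below 450 ms at baseline, no new case is 0/54, with upper limit 1 − 0.025^(1/54) = 6.6%.

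The intervals only show scale; SAP 5.1.2 plans confidence intervals for efficacy measures, not for these counts.

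**Step 5. Would a Day 0 column settle it?** Only in net terms. If two of the six men fall below 450 ms and two others rise above it, the count is 6 − 2 + 2 = 6, and the two new crossings do not show.

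**The case against.** A reader might infer that pre-existing prolongation will be reported as an effect of the drug. The documents do not support that. No passage attributes an absolute QTcF count to teverelix. Protocol 6.3.7.1 says an abnormality belonging to a pre-existing condition is not an adverse event unless it is new or worse. That safeguard is not complete: Protocol 6.3.3 and SAP 4.2.7 require any clinically significant abnormal ECG seen after dosing to be recorded as an adverse event, without mentioning baseline. Even so, neither rule turns a threshold count into a drug finding.

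Nor are the absolute criteria the only view of QT. The same list has the two change criteria, which a man with an unchanged QTcF never meets. Protocol 8.1.5 plans mean changes from baseline and normal-range shifts, and the Holter subset supports exposure-based modelling. All of this stands, and it limits the point to the counts at the absolute thresholds.

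A second objection concerns what will actually be tabulated. SAP 6.9.4 counts markedly abnormal results, which SAP 4.2.7 defines through Attachment 2, and it does not name the six QTcF thresholds. Attachment 2 and the output shells are not in the material reviewed, so they may already cross-classify by baseline. That cannot be checked, and it tempers confidence. It does not supply the missing rule in the SAP text.

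Finally, the 5% to 20% is an assumption, and the 3 to 12 men are that assumption multiplied by 60. They illustrate scale and estimate nothing.

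**Conclusion.** The point holds in a limited form. As written, SAP 4.2.7 and 6.9.4 do not separate men who newly cross 450, 480 or 500 ms from men who were above that value at baseline. The >30 and >60 ms criteria catch large rises and miss new crossings by smaller ones, and the specified shift tables do not use the 480 and 500 ms cut-offs.

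The conclusion assumes that the thresholds defined in SAP 4.2.7 are the ones tabulated, and that the unseen attachment and shells add no baseline rule. Its size cannot be computed without the baseline QTcF distribution. It concerns the clarity of a descriptive safety table. It does not show that the plan misattributes prolongation to the drug, and it is no criticism of the entry criteria.

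**What to change.** In SAP 4.2.7 and 6.9.4:

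1. Keep the >30 and >60 ms change criteria as they are.
2. Report each absolute threshold (>450, >480, >500 ms) as new onset. The denominator is men with baseline QTcF at or below that threshold, and the count is given by visit and for any post-baseline visit. Apply the same condition to the >500 ms limb of the composite.
3. Add a shift table of baseline by worst post-baseline QTcF, with categories ≤450, >450–480, >480–500 and >500 ms. Men already above a threshold at baseline then remain visible.
4. Identify men with a pacemaker in the listing where medical history or the ECG interpretation records it. Table 15 shows no paced-rhythm field, so a separate tabulation of paced ECGs should not be promised from the data described.

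The cost is SAP wording, one extra table and slightly smaller denominators for the threshold counts. The QTcF values are already collected, and eligibility does not change.
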